10.3.4. Reporting of SAEs

SAE Reporting to Pfizer Safety via an Electronic Data Collection Tool

- The primary mechanism for reporting an SAE to Pfizer Safety will be the electronic data collection tool.
- If the electronic system is unavailable, then the site will use the paper SAE data collection tool (see next section) in order to report the event within 24 hours.
- The site will enter the SAE data into the electronic system as soon as the data become available.
- After the study is completed at a given site, the electronic data collection tool will be taken off-line to prevent the entry of new data or changes to existing data.
- If a site receives a report of a new SAE from a study participant or receives updated data on a previously reported SAE after the electronic data collection tool has been taken off-line, then the site can report this information on a paper SAE form (see next section) or to Pfizer Safety by telephone.

SAE Reporting to Pfizer Safety via CT SAE Report Form

- Facsimile transmission of the CT SAE Report Form is the preferred method to transmit this information to Pfizer Safety.
- In circumstances when the facsimile is not working, notification by telephone is acceptable with a copy of the CT SAE Report Form sent by overnight mail or courier service.
- Initial notification via telephone does not replace the need for the investigator to complete and sign the CT SAE Report Form pages within the designated reporting time frames.

10.4. Appendix 4: Contraceptive Guidance

10.4.1. Male Participant Reproductive Inclusion Criteria

Male participants are eligible to participate if they agree to the following requirements during the intervention period and for at least 22 weeks after the last dose of study intervention, which corresponds to the time needed to eliminate reproductive safety risk of the study intervention(s):

- Refrain from donating sperm.

PLUS either:

- Be abstinent from heterosexual intercourse with a female of childbearing potential as their preferred and usual lifestyle (abstinent on a long-term and persistent basis) and agree to remain abstinent.

OR

- Must agree to use a male condom when engaging in any activity that allows for passage of ejaculate to another person.

10.4.2. Female Participant Reproductive Inclusion Criteria

A female participant is eligible to participate if she is not pregnant or breastfeeding, and at least 1 of the following conditions applies:

- Is not a WOCBP (see definitions below in [Section 10.4.3](#)).

OR

- Is a WOCBP and using a contraceptive method that is highly effective (with a failure rate of <1% per year), preferably with a low user dependency, as described below, during the intervention period and for at least 22 weeks after the last dose of study intervention, which corresponds to the time needed to eliminate any reproductive safety risk of the study intervention(s). If a highly effective method that is user dependent is chosen, a second effective method of contraception, as described below, must also be used. The investigator should evaluate the effectiveness of the contraceptive method in relationship to the first dose of study intervention.

- Is a WOCBP and using a contraceptive method that is highly effective (with a failure rate of <1% per year), with high user dependency, as described below during the intervention period and for at least 22 weeks after the last dose of study intervention, which corresponds to the time needed to eliminate any reproductive safety risk of the study intervention(s). In addition, a second effective method of contraception, as described below, must be used. The investigator should evaluate the effectiveness of the contraceptive method in relationship to the first dose of study intervention.

The investigator is responsible for review of medical history, menstrual history, and recent sexual activity to decrease the risk for inclusion of a woman with an early undetected pregnancy.

10.4.3. Woman of Childbearing Potential

A woman is considered fertile following menarche and until becoming postmenopausal unless permanently sterile (see below).

If fertility is unclear (eg, amenorrhea in adolescents or athletes) and a menstrual cycle cannot be confirmed before the first dose of study intervention, additional evaluation should be considered.

Women in the following categories are not considered WOCBP:

1. Premenopausal female with 1 of the following:

- Documented hysterectomy;
- Documented bilateral salpingectomy;
- Documented bilateral oophorectomy.

For individuals with permanent infertility due to an alternate medical cause other than the above, (eg, mullerian agenesis, androgen insensitivity), investigator discretion should be applied to determining study entry.

Note: Documentation for any of the above categories can come from the site personnel's review of the participant's medical records, medical examination, or medical history interview. The method of documentation should be recorded in the participant's medical record for the study.

2. Postmenopausal female:

- A postmenopausal state is defined as no menses for 12 months without an alternative medical cause. In addition, a
 - high FSH level in the postmenopausal range must be used to confirm a postmenopausal state in women under 60 years of age and not using hormonal contraception or HRT.
 - Female on HRT and whose menopausal status is in doubt will be required to use one of the nonestrogen hormonal highly effective contraception methods if they wish to continue their HRT during the study. Otherwise, they must discontinue HRT to allow confirmation of postmenopausal status before study enrollment.

10.4.4. Contraception Methods

Contraceptive use by men or women should be consistent with local availability/regulations regarding the use of contraceptive methods for those participating in clinical trials.

Highly Effective Methods That Have Low User Dependency

1. Implantable progestogen-only hormone contraception associated with inhibition of ovulation.
2. Intrauterine device.
3. Intrauterine hormone-releasing system.
4. Bilateral tubal occlusion.
5. Vasectomized partner.
 - Vasectomized partner is a highly effective contraceptive method provided that the partner is the sole sexual partner of the WOCBP and the absence of sperm has been confirmed. If not, an additional highly effective method of contraception should be used. The spermatogenesis cycle is approximately 90 days.

Highly Effective Methods That Are User Dependent

1. Combined (estrogen- and progestogen-containing) hormonal contraception associated with inhibition of ovulation:
 - Oral;
 - Intravaginal;
 - Transdermal.
2. Progestogen-only hormone contraception associated with inhibition of ovulation:
 - Oral;
 - Injectable.
3. Sexual abstinence:
 - Sexual abstinence is considered a highly effective method only if defined as refraining from heterosexual intercourse during the entire period of risk associated with the study intervention. The reliability of sexual abstinence needs to be evaluated in relation to the duration of the study and the preferred and usual lifestyle of the participant.

10.5. Appendix 5: Genetics

Use/Analysis of DNA

- Genetic variation may impact a participant's response to study intervention, susceptibility to, and severity and progression of disease. Therefore, where local regulations and IRBs/ECs allow, a blood sample will be collected for DNA analysis.
- The scope of the genetic research may be narrow (eg, 1 or more candidate genes) or broad (eg, the entire genome), as appropriate to the scientific question under investigation.
- The samples may be analyzed as part of a multistudy assessment of genetic factors involved in the response to PF-06946860 or study interventions of this class to understand treatments for the disease(s) under study or the disease(s) themselves.
- The results of genetic analyses may be reported in CSR or in a separate study summary or may be used for internal decision making without being included in a study report.
- The sponsor will store the DNA samples in a secure storage space with adequate measures to protect confidentiality.
- The samples will be retained as indicated:
 - Samples for banking will be stored indefinitely or for another period as per local requirements.
 - Participants may withdraw their consent for the storage and/or use of their Banked Biospecimens at any time by making a request to the investigator; in this case, any remaining material will be destroyed. Data already generated from the samples will be retained to protect the integrity of existing analyses.
 - Banked Biospecimens will be labeled with a code. The key between the code and the participant's personally identifying information (eg, name, address) will be held at the study site and will not be provided to the sample bank.

10.6. Appendix 6: Liver Safety: Suggested Actions and Follow-up Assessments

Potential Cases of Drug-Induced Liver Injury

Humans exposed to a drug who show no sign of liver injury (as determined by elevations in transaminases) are termed “tolerators,” while those who show transient liver injury, but adapt are termed “adaptors.” In some participants, transaminase elevations are a harbinger of a more serious potential outcome. These participants fail to adapt and therefore are “susceptible” to progressive and serious liver injury, commonly referred to as DILI. Participants who experience a transaminase elevation above $3 \times$ ULN should be monitored more frequently to determine if they are an “adaptor” or are “susceptible.”

In the majority of DILI cases, elevations in AST and/or ALT precede TBili elevations ($>2 \times$ ULN) by several days or weeks. The increase in TBili typically occurs while AST/ALT is/are still elevated above $3 \times$ ULN (ie, AST/ALT and TBili values will be elevated within the same laboratory sample). In rare instances, by the time TBili elevations are detected, AST/ALT values might have decreased. This occurrence is still regarded as a potential DILI. Therefore, abnormal elevations in either AST OR ALT in addition to TBili that meet the criteria outlined below are considered potential DILI (assessed per Hy’s law criteria) cases and should always be considered important medical events, even before all other possible causes of liver injury have been excluded.

The threshold of laboratory abnormalities for a potential DILI case depends on the participant’s individual baseline values and underlying conditions. Participants who present with the following laboratory abnormalities should be evaluated further as potential DILI (Hy’s law) cases to definitively determine the etiology of the abnormal laboratory values:

- Participants with AST/ALT and TBili baseline values within the normal range who subsequently present with AST OR ALT values $>3 \times$ ULN AND a TBili value $>2 \times$ ULN with no evidence of hemolysis and an alkaline phosphatase value $<2 \times$ ULN or not available.
- For participants with baseline AST **OR** ALT **OR** TBili values above the ULN, the following threshold values are used in the definition mentioned above, as needed, depending on which values are above the ULN at baseline:
 - Preexisting AST or ALT baseline values above the normal range: AST or ALT values >2 times the baseline values AND $>3 \times$ ULN; or $>8 \times$ ULN (whichever is smaller).
 - Preexisting values of TBili above the normal range: TBili level increased from baseline value by an amount of at least $1 \times$ ULN **or** if the value reaches $>3 \times$ ULN (whichever is smaller).

Rises in AST/ALT and TBili separated by more than a few weeks should be assessed individually based on clinical judgment; any case where uncertainty remains as to whether it represents a potential Hy's law case should be reviewed with the sponsor.

The participant should return to the investigator site and be evaluated as soon as possible, preferably within 48 hours from awareness of the abnormal results. This evaluation should include laboratory tests, detailed history, and physical assessment. The possibility of hepatic neoplasia (primary or secondary) should be considered.

In addition to repeating measurements of AST and ALT and TBili for suspected cases of Hy's law, additional laboratory tests should include albumin, CK, direct and indirect bilirubin, GGT, PT/INR, total bile acids, and alkaline phosphatase. Consideration should also be given to drawing a separate tube of clotted blood and an anticoagulated tube of blood for further testing, as needed, for further contemporaneous analyses at the time of the recognized initial abnormalities to determine etiology. A detailed history, including relevant information, such as review of ethanol, acetaminophen/paracetamol (either by itself or as a coformulated product in prescription or over-the-counter medications), recreational drug, supplement (herbal) use and consumption, family history, sexual history, travel history, history of contact with a jaundiced person, surgery, blood transfusion, history of liver or allergic disease, and potential occupational exposure to chemicals, should be collected. Further testing for acute hepatitis A, B, C, D, and E infection and liver imaging (eg, biliary tract) and collection of serum samples for acetaminophen/paracetamol drug and/or protein adduct levels may be warranted.

All cases demonstrated on repeat testing as meeting the laboratory criteria of AST/ALT and TBili elevation defined above should be considered potential DILI (Hy's law) cases if no other reason for the LFT abnormalities has yet been found. **Such potential DILI (Hy's law) cases are to be reported as SAEs, irrespective of availability of all the results of the investigations performed to determine etiology of the LFT abnormalities.**

A potential DILI (Hy's law) case becomes a confirmed case only after all results of reasonable investigations have been received and have excluded an alternative etiology.

[figure not shown]
10.7. Appendix 7: Cancer-Related Cachexia Symptom Assessment – Appetite

On average, how would you rate your appetite during the past 7 days?

										
0	1	2	3	4	5	6	7	8	9	10
No appetite										Very good appetite

10.8. Appendix 8: Cancer-Related Cachexia Symptom Assessment – Fatigue

On average, how would you rate your physical fatigue during the past 7 days?

10.9. Appendix 9: PROMIS Pain 1a

Pain Intensity – 1a

Please respond to the question by marking one box.

Pain Intensity
In the past 7 days...

How would you rate your pain on average?

										
0	1	2	3	4	5	6	7	8	9	10
No pain										
Worst imaginable pain										

10.10. Appendix 10: Patient Global Impression of Change

Compared to before you started the study, how would you rate your appetite now?

- Much better
- Moderately better
- A little better
- No change
- A little worse
- Moderately worse
- Much worse

Compared to before you started the study, how would you rate your physical fatigue now?

- Much better
- Moderately better
- A little better
- No change
- A little worse
- Moderately worse
- Much worse

10.11. Appendix 11 Study Conduct

10.11.1. Telehealth Visits

Telehealth visits may be conducted during this study and used to assess participant safety and collect data points. Telehealth includes the exchange of healthcare information and services via telecommunication technologies (eg, audio, video, video-conferencing software) remotely, allowing the participant and the investigator to communicate on aspects of clinical care, including medical advice, reminders, education, and safety monitoring. Assessments to be performed during a telehealth visit are outlined in the [SoA](#), and may include:

- Review and record study intervention(s), including compliance and missed doses.
- Review and record any AEs and SAEs since the last contact. Refer to [Section 8.3](#).
- Review and record any new concomitant medications or changes in concomitant medications since the last contact.
- Review and record contraceptive method and results of pregnancy testing. Confirm that the participant is adhering to the contraception method(s) required in the protocol. Refer to [Appendix 4](#).

Study participants must be reminded to promptly notify site staff about any change in their health status.

10.11.2. Nutritional Advice Consult

If operationally feasible, a nutritional consult with a registered dietician via telehealth with a central vendor will be scheduled by the participant within the first 7 days after randomization.

10.11.3. Home Health Visits

A home health care service may be utilized to facilitate scheduled visits per the [Schedule of Activities](#). Home health visits include a healthcare provider conducting an in-person study visit at the participant's location, rather than an in-person study visit at the site. Additional details will be provided separately.

10.12. Appendix 12 Alternative Measures During Public Emergencies

The alternative study measures described in this section are to be followed during public emergencies, including the COVID-19 pandemic. This appendix applies for the duration of the COVID-19 pandemic globally and will become effective for other public emergencies only upon written notification from Pfizer.

Use of these alternative study measures are expected to cease upon the return of business as usual circumstances (including the lifting of any quarantines and travel bans/advisories).

10.12.1. Eligibility

While SARS-CoV2 testing is not mandated for this study, local clinical practice standards for testing should be followed. A patient should be excluded if he/she has a positive test result for SARS-CoV2 infection, is known to have asymptomatic infection, or is suspected of having SARS-CoV2. Patients with active infections are excluded from study participation as per protocol language regarding eligibility exclusions due to infection.

10.12.2. Adverse Events and Serious Adverse Events

If a participant has COVID-19 during the study, this should be reported as an adverse event (AE) or serious adverse event (SAE) and appropriate medical intervention provided. The participant should be discontinued from the study. Study treatment should continue unless the investigator/treating physician is concerned about the safety of the participant, in which case temporary or permanent discontinuation may be required. It is recommended that the investigator discuss permanent discontinuation of study intervention with the study medical monitor.

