1.2. Schema

1.3. Schedule of Activities

The SoA table provides an overview of the protocol visits and procedures. Refer to the **STUDY ASSESSMENTS AND PROCEDURES** section of the protocol for detailed information on each procedure and assessment required for compliance with the protocol.

The investigator may schedule visits (unplanned visits) in addition to those listed in the SoA table, in order to conduct evaluations or assessments required to protect the well-being of the participant.

	Screening	Part A: Double-Blind					Part B: Open-Label						Part A: Follow-up ^b	Part B: Follow-up ^c	Early Term/ Discontinuation
Visit Identifier	v1	v2	v3	v4	v5	v6	v7	v8	v9	v10	v11	v12	v13		
Abbreviations, see Appendix 13															
Study Week (relative to Day 1)		Rand	wk3	wk4 ^{a,b}	wk6	wk9	wk12	wk15	wk18	wk21	wk24				
Study Day (relative to Day 1 dosing)	-28 to -5	Day 1	22	29	43	64	85	106	127	148	169	50	197		
Visit Window (days)			±1	±1	±1	±3	±3	±3	±3	±3	±3	+7	+7		
Clinic Visit	X	X													
Telehealth Visit ^d			X	X	X		X		X		X	X	X	X	X
At-Home/Residential Care Facility Home-HCP Visit ^d			X	X	X	X	X	X	X	X	X	X	X	X	X
Informed Consent and Registration	X														
Informed consent (caregiver) ^e	X														
Review of Eligibility Criteria	X	X													
Randomization		X													
Administration of blinded PF-06946860/placebo		X	X												
Administration of open-label PF-06946860					X	X	X	X	X	X	X				
Medical History, Demography and Height	X														
Record Prior or Concomitant treatments	X	X	→	→	→	→	→	→	→	→	→	→	X	X	X
Monitor Serious/nonserious AEs	X	X	→	→	→	→	→	→	→	→	→	→	X	X	X
Review contraception use	X	X	X		X	X	X	X	X	X	X	X	X	X	X
Physical Examination (Height at Screening only) ^f	X												X	X	X
PRO (weekly) 7-day recall: appetite, fatigue, pain ^g	X	X ^h	→	→	→	→ ⁱ	→ ⁱ	→ ⁱ	→ ⁱ	→ ⁱ	→ ⁱ	→ ⁱ	X ⁱ	X ⁱ	X
PRO PGI-C: appetite and fatigue				X	X								X ⁱ		X
Qualitative Phone Interview (participant) ^j				X ⁱ		X ⁱ									X ⁱ
Qualitative Phone Interview (care giver) ^{e,j}				X											X
Weight + Body Composition via BIA (BIA not at Screen)	X	X ^h	X ⁱ	X ⁱ	X ⁱ	X ⁱ	X ⁱ	X ⁱ	X ⁱ	X ⁱ	X ⁱ	X ⁱ	X ⁱ	X ⁱ	X
Blood and Urine samples: Clinical Lab Tests, Table 2	X	X	X		X	X	X	X	X	X	X	X	X	X	X
Pregnancy Test for female participants of childbearing potential (Blood and/or Urine)	X	X			X		X		X		X				
Blood sample for GDF-15 ^k	X	X	X	X	X		X ⁱ		X ⁱ		X ⁱ	X ⁱ	X ⁱ	X ⁱ	X
Blood sample for PF-06946860 PK ^k		X	X	X	X		X ⁱ		X ⁱ		X ⁱ	X ⁱ	X ⁱ	X ⁱ	X

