4.2.2. Duration of Dosing

The double-blind portion of this study (Part A) will be 6 weeks in duration. This is anticipated to be sufficient to detect an effect on the primary endpoint, appetite, while minimizing the required duration of study participation.

All participants completing the 6-week double-blind portion of the study will be given the option of receiving open-label PF-06946860 during study Part B. As efficacy has not yet been studied in a clinical setting, participation in study Part B will be optional with the purpose of providing continued access to participants who are deriving or may derive benefit (based on their own perception, along with that of their investigator).

The total duration of dosing with PF-06946860 in this study will be up to 24 weeks, as supported by completed nonclinical toxicity studies ([Section 2.2.1](#)).

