6.1.1. Administration

Each dose of investigational product must be administered by appropriately qualified health care personnel (whether administered at home or in a clinic setting). During the double-blind portion (Part A) of the study, investigational product will be administered at a dose of **CCI** or placebo Q3W SC for a total of 2 doses (6 weeks). If the participant continues to the optional OLT period (Part B), up to 7 additional doses of PF-06946860 **CCI** will be administered starting at the Week 6 visit (for participants entering the OLT period). Each dose is comprised of two 1 mL SC injections which are to be administered consecutively. For participants who are receiving standard of care systemic antineoplastic treatment, premedication is permitted consistent with institutional guidelines, and, unless specifically noted in [Section 6.5](#), may include an antihistamine, anti-inflammatory agent, or pain reliever. In such cases, PF-06946860 is to be administered first, followed by any required premedications. If the standard of care systemic antineoplastic treatment is to be administered on the same day of dosing with study drug (PF-06946860 or placebo in Part A or PF-06946860 in Part B), where feasible, the study drug will be administered prior to the standard of care antineoplastic treatment.

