6.2. Preparation/Handling/Storage/Accountability

1. The investigator or designee must confirm appropriate temperature conditions have been maintained during transit for all study interventions received and any discrepancies are reported and resolved before use of the study intervention.
2. Only participants enrolled in the study may receive study intervention and only authorized site staff or designated healthcare personnel may supply or administer study intervention. All study interventions must be stored in a secure, environmentally controlled, and monitored (manual or automated recording) area in accordance with the labeled storage conditions with access limited to the investigator and authorized site staff. At a minimum, daily minimum and maximum temperatures for all site storage locations must be documented and available upon request. Data for nonworking days must indicate the minimum and maximum temperatures since previously documented for all site storage locations upon return to business.
3. Any excursions from the study intervention label storage conditions should be reported to Pfizer upon discovery along with any actions taken. The site should actively pursue options for returning the study intervention to the storage conditions described in the labeling, as soon as possible. Once an excursion is identified, the study intervention must be quarantined and not used until Pfizer provides permission to use the study intervention. Specific details regarding the definition of an excursion and information the site should report for each excursion will be provided to the site in the IP manual.
4. Any storage conditions stated in the SRSD will be superseded by the storage conditions stated on the label.
5. Study interventions should be stored in their original containers.

6. The investigator, institution, or the head of the medical institution (where applicable) is responsible for study intervention accountability, reconciliation, and record maintenance (ie, receipt, reconciliation, and final disposition records), such as the IPAL or sponsor-approved equivalent. All study interventions will be accounted for using a study intervention accountability form/record. All study intervention that is administered at home by the designated healthcare personnel, both used and unused, must be returned to the investigator by the designated healthcare personnel. Returned study intervention must not be redispensed to the participants.

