6.3. Measures to Minimize Bias: Randomization and Blinding

6.3.1. Allocation to Study Intervention

Allocation of participants to treatment groups will proceed through the use of an IRT system (IWR). The site personnel (study coordinator or specified designee) will be required to enter or select information including, but not limited to, the user's ID and password, the protocol number, and the participant number. The site personnel will then be provided with a treatment assignment, randomization number, and DU or container number when study intervention is being supplied via the IRT system. The IRT system will provide a confirmation report containing the participant number, randomization number, and DU or container number assigned. The confirmation report must be stored in the site's files.

Study intervention will be administered at the study visits summarized in the **SoA**.

The study-specific IRT reference manual and IP manual will provide the contact information and further details on the use of the IRT system.

In the event of a Quality Assurance audit, the auditor(s) will be allowed access to unblinded study intervention records at the site(s) to verify that randomization/dispensing has been done accurately.

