7.2. Participant Discontinuation/Withdrawal From the Study

A participant may withdraw from the study at any time at his/her own request. Reasons for discontinuation from the study include the following:

- Refused further follow-up;
- Lost to follow-up;
- Death;
- Study terminated by sponsor.

At the time of discontinuing from the study, if possible, an early discontinuation visit should be conducted. See the [SoA](#) for assessments to be collected at the time of study discontinuation and follow-up and for any further evaluations that need to be completed.

If a participant withdraws from the study, he/she may request destruction of any remaining samples taken and not tested, and the investigator must document any such requests in the site study records and notify the sponsor accordingly.

If the participant withdraws from the study and also withdraws consent (see [Section 7.2.1](#)) for disclosure of future information, no further evaluations should be performed and no additional data should be collected. The sponsor may retain and continue to use any data collected before such withdrawal of consent.

Lack of completion of all or any of the withdrawal/early termination procedures will not be viewed as protocol deviations so long as the participant's safety was preserved.

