9.1. Estimands and Statistical Hypotheses

9.1.1. Estimands

*Estimand related to the **appetite** primary objective:*

Estimand 1 (similar to “hypothetical”) is intended to provide a population level estimate of the treatment effect on the change from baseline Appetite score for PF-06946860 compared to placebo in all evaluable participants under the scenario of no discontinuation of study intervention and without the potential confounding effects of prohibited medications, regardless of the participants’ compliance with dosing (ie, using the Censored analysis set).

- Population: Patients with advanced cancer, anorexia and elevated circulating GDF-15 levels.

- Variable: Change from baseline for the patient reported 7-day recall Cancer-Related Cachexia Symptom Assessment-Appetite score at Week 4.
- Intercurrent Events:
 - a. Discontinuation of study intervention - Data collected after a participant has discontinued study intervention will be censored and treated as missing data.
 - b. Prohibited medications - Data collected after a participant has received prohibited medications, that would modulate the primary endpoint, will be censored and treated as missing data. The list of concomitant medications will be reviewed prior to database lock to determine which would be classed as “prohibited” for this estimand.
 - c. Inadequate compliance - Data collected after a participant has missed a dose will be censored and treated as missing data.

Missing data due to censoring, study withdrawal or other reasons, are assumed to be missing at random.

- Population level summary: Difference in mean change from baseline for the patient reported 7-day recall Cancer-Related Cachexia Symptom Assessment-Appetite score at Week 4 between PF-06946860 and placebo.

This estimand will similarly be applied to the appetite secondary objective (ie, change from baseline at Weeks 1, 2, 3, 5 and 6).

Alternative estimands for the primary objective may be used in order to examine the robustness of the results and will be detailed in the SAP.

Estimand related to the fatigue secondary objective:

Estimand 2 will be similar to Estimand 1, except for the following:

- Variable: Change from baseline for the patient reported 7-day recall Cancer-Related Cachexia Symptom Assessment-Fatigue score at Weeks 1, 2, 3, 4, 5 and 6.

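### Protocol 10.12.2 tells sites to take a participant with COVID-19 out of the study and also to keep dosing; the exit sentence also conflicts with Section 7.1 and is probably a drafting slip

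*Protocol*

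**What the plan says.** Protocol Section 10.12.2 first requires COVID-19 to be reported as an adverse event and treated. It then says: "The participant should be discontinued from the study. Study treatment should continue unless the investigator/treating physician is concerned about the safety of the participant". The rest of that sentence allows a temporary or permanent stop of drug where there is a safety concern. The next sentence recommends discussing a permanent stop with the medical monitor. Under Section 10.12 the appendix is in force for the whole COVID-19 pandemic; only other emergencies need written notice from the sponsor.

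The related rules in the protocol are:

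- **Dosing (6.3.1):** "Study intervention will be administered at the study visits summarized in the" schedule of activities.
- **Stopping drug (7.1):** stopping drug is a different event from leaving the study, and a participant who stops permanently stays under study follow-up.
- **Participant asks to stop drug (7.2.1):** the same, unless consent to further contact is withdrawn.
- **Leaving the study (7.2):** "At the time of discontinuing from the study, if possible, an early discontinuation visit should be conducted". Nothing provides for dosing afterwards.
- **Open-label access (4.2.2):** "All participants completing the 6-week double-blind portion of the study will be given the option of receiving open-label PF-06946860 during study Part B".

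**The concern.** The first sentence is unconditional: every participant with COVID-19 leaves the study. The second makes continued dosing the default. An investigator whose patient has a mild infection and no safety concern cannot do both.

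This is an operative rule for site staff. If the first sentence is obeyed, patients who could have continued safely are removed, with two consequences. The trial may lose a Week 4 appetite score, which is the primary endpoint, and Section 9.2 says withdrawals are not replaced. The patient also loses any remaining doses, including the optional open-label treatment. If different sites obey different sentences, similar patients are handled differently.

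**Working it through.** No formula applies and the plan states no figure to reproduce. The check takes each outcome that 10.12.2 allows for drug and asks whether exit from the study is compatible with it.

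| Outcome for drug | Compatible with exit? | Reason |
|---|---|---|
| Continued (no safety concern) | No | Dosing takes place at study visits (6.3.1), and a participant who has left has none |
| Paused (safety concern) | No | A pause implies possible resumption, which needs study visits |
| Permanently stopped (safety concern) | Within 10.12.2, yes; with 7.1, no | 7.1 keeps the participant in follow-up; 7.2.1 takes the same line |

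The exit sentence conflicts with some part of the protocol in all three rows. The treatment sentences conflict with nothing except the exit sentence. That is why the exit sentence looks like the error.

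The schedule shows what one removed participant would lose. These counts apply to any early exit, whatever the reason. They do not measure how often this conflict would matter.

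*Appetite scores.* The schedule lists "PRO (weekly) 7-day recall: appetite, fatigue, pain". The nominal day for Week w is 7w + 1, so Weeks 1 to 6 fall on Days 8, 15, 22, 29, 36 and 43. The Week 4 window is 29 ± 1, or Days 28 to 30.

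- Exit before Day 8: Weeks 1 to 6 are lost (6 of 6), including the primary score.
- Exit on Days 23 to 27: Weeks 4, 5 and 6 are lost (3 of 6), including the primary score.
- Exit on Days 28 to 30: the early-termination visit includes the appetite question, so a score taken then falls inside the Week 4 window and the primary score may be kept.
- Exit on Days 31 to 35, with Week 4 already recorded: Weeks 5 and 6 are lost (2 of 6) and the primary score is kept.

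An early-termination score taken before Day 28 would not usually stand in for Week 4. I found no rule in either document that assigns such a score to a planned week.

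*Doses.* Part A has 2 blinded doses, and Section 6.1.1 allows "up to 7 additional doses of PF-06946860" in Part B, so the maximum is 2 + 7 = 9. Exit after the first dose and before the second forgoes up to 1 + 7 = 8 of 9. Exit after the second dose but still in Part A forgoes up to 7. It is 'up to' because Part B is optional.

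*Effect of staying in the study.* Retention does not guarantee a usable primary score. Under Estimand 1 (9.1.1) the Week 4 score is censored if, before it is taken, the participant stops drug or misses a dose. The same applies to certain medication: "Data collected after a participant has received prohibited medications, that would modulate the primary endpoint, will be censored and treated as missing data". In those cases the score serves only Estimand 3, which SAP Section 2.1.3 makes optional.

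**The case against.** The strongest reply is that the intent is plain and the practical risk small. Sections 7.1 and 7.2.1 show that staying in the study is the general rule, and the treatment sentences in 10.12.2 make sense mainly for someone still in the study. Section 8 requires safety issues to be discussed with the sponsor at once, so a site is unlikely to act alone. Adverse-event follow-up continues (8.3.1, 8.3.3), and scores already collected stay in the repeated-measures model. Section 9.2 already allows for 25% discontinuation, from about 40 randomized to about 30 completing.

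Most of this stands, and it is why the point is minor. It does not correct the text. The Section 8 discussion concerns continuing or stopping study intervention, not leaving the study, and 10.12.2 only recommends contact with the medical monitor about a permanent stop.

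A reader might infer more than the documents support:

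- *That the trial loses power or is biased.* With no COVID-19 rate given, neither can be derived.
- *That Section 7.2 forbids exit for COVID-19.* COVID-19 is not among its listed reasons, but the list is not written as exhaustive.
- *That Section 6.2 alone bars dosing after exit.* It says "Only participants enrolled in the study may receive study intervention", but Section 9.3 defines enrolment by agreement to participate after consent and does not say that this status ends on leaving. The visit-based dosing rule in 6.3.1 is the firmer support.
- *That steroid treatment for COVID-19 would necessarily censor the score.* Section 6.5 prohibits starting systemic glucocorticoids in Part A, but 9.1.1 leaves the list of censoring medications to a review before database lock.

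**Conclusion.** Wrong as written; minor. That the sentences conflict is certain from the text. That the exit sentence is a slip is a strong inference from Sections 7.1 and 7.2.1, but the documents do not state the intent.

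The consequence is per participant. Literal compliance removes people with no safety concern, usually costs the primary score if exit comes before Day 28, and ends open-label access or the remaining open-label doses. How many would be affected is unknown and likely small.

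The conclusion rests on two assumptions: that leaving the study in 10.12.2 means what Section 7.2 describes, and that drug is supplied only at scheduled study visits. No section says otherwise on either.

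**What to change.** The sponsor should first confirm that retention is intended. The exit sentence in 10.12.2 is then replaced with: *The participant need not be discontinued from the study; if study intervention is permanently discontinued, Section 7.1 applies.* The treatment sentences that follow stay as they are. This wording leaves Section 7.1 and the schedule of activities to decide what is collected after a permanent stop, and does not impose the full visit schedule on every case.

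If exit really is intended, deleting the sentence on continued treatment would not be enough. The provision for a pause would also have to go, and Section 7.1 would need an exception.

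The cost is one sentence, issued as an amendment with IRB/EC approval (Section 10.1.1), or as an administrative letter if the sponsor and IRB/EC accept that. No participants, analyses or visits beyond the existing schedule are added. The SAP needs no change, because stopped drug, missed doses, prohibited medication and withdrawal are already covered there.
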